## **6. STUDY ASSESSMENTS AND PROCEDURES**

A schedule of study assessments and tests is shown in [Table 2](#). The details of study assessments are shown in “Study Procedures Manual” that sponsor prepared separately.

The time assessment window of the each PK blood sample collection is shown in [Table 3](#). The end time of the infusion will be designated Time 0, and subsequent PK sampling and safety assessments will be performed relative to this time. It is essential that the exact time of blood sampling, however, should still be accurately recorded. The safety assessments are recommended to be conducted close to PK sample collection; however, when several procedures are scheduled at the same nominal time point, PK blood sampling should be given priority.

**Table 2 Time and Events Table**

Visit	1	2						3	4	5	6	7	8	9	10	
Day	Screening Day -30 to -1	Day 0						Day 1	Day 7	Day 14	Day 21	Day 28	Day 42	Day 56	Day 84	Discontinuation 
		Pre	0	5m	1h	6h	24h									
Informed consent 	X															
Medical History	X	X														
Demography	X															
Inclusion/Exclusion criteria	X	X 														
Complete physical examination, including Height	X															
Body weight		X														
Vital signs 	X	X	X	X	X	X	X	X	X	X	X	X	X	X	X	X
Record Concomitant Medications	X	X	X	X	X	X	X	X	X	X	X	X	X	X	X	X
Clinical Laboratory test 	X	X 					X			X		X		X	X	X
Spot urine (protein to creatinine ratio)	X															
Urine drug/alcohol screen	X															
HIV, Hepatitis B, C 	X															
Pregnancy test (women) 	X	X 										X			X	X
Chest X ray	X															
12 lead ECG	X	X 					X								X	X
Biological Markers 	X 	X								X		X	X	X	X	
Blood PK sampling		X		X	X	X	X	X	X	X	X	X	X	X	X	

Visit	1	2						3	4	5	6	7	8	9	10	
Day	Screening Day -30 to -1	Day 0						Day 1	Day 7	Day 14	Day 21	Day 28	Day 42	Day 56	Day 84	Discontinuation 
		Pre	0	5m	1h	6h	24h									
AE/SAE Review 	X	X	X	X	X	X	X	X	X	X	X	X	X	X	X	X
Admission to Unit		X 														
Dosing			X													
Discharge							X 									
Outpatient Visit	X							X	X	X	X	X	X	X	X	X

1. Each subject must sign an informed consent form prior to undergoing any Screening assessments.
2. Clinical laboratory test at screening visit will be used for inclusion/exclusion criteria check.
3. Vital signs include temperature, sitting blood pressure and heart rate. Pulse rate could be used to replace heart rate monitoring if subject has regular sinus rhythm.
4. Clinical Laboratory test include hematology, chemistry and urinalysis (including C-reactive protein [CRP] and Erythrocyte Sedimentation Rate on screening). ALT and/or AST elevations of greater than 2.5 x ULN will require additional Hepatitis B assessment, see Section 6.2.1.1. For pre-dose safety lab monitoring including urine pregnancy test and 12 lead ECG, it's recommended to be done on day 0 or within 48 hours prior to day 0 if site logistic management are limited on day 0 for drug dosing and intensive PK sample collection.
5. HIV antibody, Hepatitis B surface antigen, anti-HBc and Hepatitis C antibody.
6. Pregnancy should be assessed with a blood test at Screening and with a urine test during the treatment period. Pregnancy beyond Day 84 and within 16 weeks after last dose of IP will be assessed with a homekit and subjects can report the results via phone to site.
7. Biomarkers include immunoglobulins, B cell subsets (CD20+, CD20+/27+ memory, CD20+/27-naïve, CD20+/69+ activated, CD20+/138+ plasmacytoid, CD19+/27BRIGHT/38BRIGHT SLE subset and CD20-/138+ plasma cells).
8. Only immunoglobulins (IgG, IgM and IgA) and auto antibodies (anti-dsDNA, ANA).
9. Includes subject history to be reported on CRF regarding any general signs or symptoms of infection.
10. The recommended date of "Admission to the Unit" and "Discharge" is only a suggestion. The subject can be admitted to unit from Day -2 to Day 0 and/or discharged on Day 1 based on site flexibility and resource allocation.
11. If a subject prematurely withdraws for any reason, the investigator must make every effort to assess the items specified on discontinuation test.

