## **9.2. Sample Size Considerations**

### **9.2.1. Sample Size Assumptions**

There are no formal calculations of power or sample size for this study. The sample size of 20 to obtain 12 evaluable subjects has been chosen based on feasibility, as well as to meet requirement of [China FDA, 2005](#) (CFDA Guidance).

With 12 evaluable subjects in this study, assuming that the CV% of Cmax and AUC(0-inf) is 20.0% and 32.1% respectively (from study C1105), it is estimated that the lower and upper bounds of the 95% confidence interval would lie within 13.4% of the point estimate for Cmax and 22.0% of the point estimate for AUC(0-inf). This is narrower than the Japan study BEL114243, in which the 95% confidence interval lied within 15.0% of the point estimate for Cmax and 33.7% of the point estimate for AUC (0-inf).

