5. ANALYSIS POPULATIONS

Population	Definition / Criteria	Analyses Evaluated
Safety	
 Subjects who receive at least one dose of study medication. 	
 Study Population Safety
Pharmacokinetic Concentration Population	
 Subjects who receive the study medication and for whom a pharmacokinetic sample is obtained and analysed. 	
 PK Analyses
Pharmacokinetic Parameter Population	
 Subjects who receive a dose of GSK1550188 and for whom pharmacokinetic parameters can be calculated. 	
 PK Analyses
Pharmacodynamic Population	
 Subjects who receive the study medication and for whom pharmacodynamic data are available. 	
 PD Analyses

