11.5. Appendix 5: Premature Withdrawals & Handling of Missing Data

11.5.1. Premature Withdrawals

Element	Reporting Detail
General	
 • Subject study completion (i.e. as specified in the protocol) was defined as completion of all the phases of the study including the follow up visit. • Withdrawn subjects were not replaced in the study. • All subjects who withdraw prematurely from the study will be documented and the reason for their withdrawal recorded in the final Clinical Pharmacology Study Report (CPSR). • All available data from subjects who were withdrawn from the study will be listed and all available planned data will be included in summary, tables and figures, unless otherwise specified. • In the event that the study is prematurely discontinued, all available data will be listed and a review carried out by the study team to assess which statistical analyses are still considered appropriate and population approach may be used to deal with such situations as appropriate.

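### The discontinuation visit takes no PK or B-cell sample, and truncated PK profiles are pooled with Day 84 completers without a rule. AUC(0-t) is biased low for last samples before about Day 56, terminal-phase parameters before about Day 21 to 28.

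*Protocol*

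**What the plan says.** PK is the primary objective, and the effect on B-cell subsets is a secondary one (protocol section 2). Footnote 11 of protocol Table 2 governs early withdrawal: "If a subject prematurely withdraws for any reason, the investigator must make every effort to assess the items specified on discontinuation test". The Discontinuation column is marked for vital signs, concomitant medications, clinical laboratory tests, pregnancy test, ECG and AE review. It is blank in the "Blood PK sampling" row and in the Biological Markers row. SAP 11.1.1 has the same blanks, and protocol 6.3 and 6.4 list scheduled times only.

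The one exception is a PK sample after a liver event. Section 6.2.1 asks for it one to two weeks after the event. Appendix 1 ties it to the Time and Events Table. The two must be reconciled.

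On the analysis side, SAP section 5 defines the PK Parameter Population as "Subjects who receive a dose of GSK1550188 and for whom pharmacokinetic parameters can be calculated". SAP 11.5.1 says of withdrawn subjects that "all available planned data will be included in summary, tables and figures, unless otherwise specified", and that they are not replaced. AUC(0-t) runs to each subject's own last quantifiable time (SAP 8.1.3). Neither document gives a minimum profile length, a lambda_z acceptance criterion, a limit on extrapolated area or a sensitivity summary.

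**The concern.** A site that follows the schedule exactly draws safety blood from a withdrawing subject and takes no tube for the primary endpoint. The last PK point is then the last scheduled visit attended, up to 28 days earlier (Day 56 to Day 84). That sample cannot be recovered later.

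The short profile then enters the summaries. An AUC(0-t) that stops at Day 14 is averaged with one that runs to Day 84, although the two measure different things. If lambda_z is fitted partly to distribution-phase samples, it passes its error to t1/2, AUC(0-inf), CL and Vz. These estimates are meant to support registration in China (protocol 1.2) and, if needed, comparison with non-Chinese subjects (protocol 3.3.1).

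**Working it through.** **The plan's own precision.** Protocol 9.2.1 assumes a CV that "is 20.0% and 32.1% respectively (from study C1105") for Cmax and AUC(0-inf), with 12 evaluable subjects. On the log scale SD = sqrt(ln(1+CV²)), which gives 0.198 and 0.313. The upper bound relative to the geometric mean is exp(t × SD/√n) − 1 with t(0.975, 11) = 2.201. This gives 13.4% and 22.0%, as stated. With all 20 subjects it would be 9.7% and 15.8%. The precision statement therefore already allows 8 losses, and what remains to examine is bias.

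**Inputs.** Terminal half-life 19.4 days and distribution half-life 1.1-1.8 days (protocol 1.1.2); nominal hours from protocol Table 3, so the Day 14 sample is at 360 h (15 days) and Day 84 at 2040 h (85 days). Assumption not in the documents: a fraction f = 0.4-0.7 of the initial concentration belongs to the distribution phase.

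**Formulas.** C(t) = f·exp(−αt) + (1−f)·exp(−βt), with α = ln2/1.1 to ln2/1.8 and β = ln2/19.4 = 0.0357 per day. AUC(0-t) = (f/α)(1−exp(−αt)) + ((1−f)/β)(1−exp(−βt)). If r is the ratio of a truncated AUC(0-t) to a Day 84 completer's, k truncated profiles among n change the geometric mean by r^(k/n) − 1. For lambda_z, I fitted a log-linear line to the last three nominal samples, and AUC(0-inf) = AUC(0-t) + C(t)/lambda_z.

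**Worked case, last sample Day 14, 1 of 12.**
- f = 0.4, 1.1 days: AUC to 15 days 7.60, to 85 days 16.62, total 17.43. Captured 7.60/17.43 = 44%. r = 0.457, and 0.457^(1/12) − 1 = −6.3%.
- f = 0.7, 1.8 days: 5.30, 9.81 and 10.21. Captured 52%. r = 0.540, shift −5.0%.

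**All visits, over the assumed range.**

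| Last PK sample | True AUC captured | Geometric mean AUC(0-t), 1 of 12 | Subject's t1/2 (true 19.4 d) | Subject's AUC(0-inf), % of true |
|---|---|---|---|---|
| 24 h | 5-9% | −18 to −22% | not computed | not computed |
| Day 7 | 28-37% | −7.6 to −9.8% | 4.6-9.3 d | 51-62% |
| Day 14 | 44-52% | −5.0 to −6.3% | 7.5-14 d | 71-84% |
| Day 21 | 56-62% | −3.5 to −4.3% | 15.3-19.2 d | 92-99.5% |
| Day 28 | 66-71% | −2.5 to −3.0% | 18.9-19.4 d | 99-100% |
| Day 42 | 79-82% | −1.3 to −1.5% | 19.4 d | 100% |
| Day 56 | 87-89% | −0.6 to −0.7% | 19.4 d | 100% |
| Day 84 | 95-96% | reference | 19.4 d | 100% |

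Because CL = dose/AUC(0-inf), a Day 7 truncation inflates that subject's CL by 60-97% (1/0.624 to 1/0.507). In the pooled geometric mean AUC(0-inf), one such subject in 12 costs 3.9-5.5%, and one Day 14 truncation costs 1.4-2.9%.

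A separate simulation with 10% residual error and lambda_z from at least three points (both assumed) gave AUC(0-inf) ratios to true of 0.81 at Day 14, 0.98 at Day 28 and 1.01 at Day 56. The t1/2 ratios were 0.63, 0.90 and 0.99. Noise therefore leaves t1/2 somewhat low at Day 28.

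**What a discontinuation sample recovers (AUC(0-t), 1 of 12).**
- Last sample Day 14, withdrawal at day 21: −5.0 to −6.3% becomes −3.7 to −4.6%, about a quarter removed.
- Last sample Day 28, withdrawal at day 42: −2.5 to −3.0% becomes −1.3 to −1.6%, a little under half removed.
- Last sample 24 h, withdrawal at day 7: −18 to −22% becomes −8 to −11%, about half removed.

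**The case against.** The strongest reply is that few withdrawals would do harm. Cmax is set on Day 0. From Day 28 AUC(0-inf) is practically unbiased, and a Day 56 truncation barely moves AUC(0-t). Scheduled ECGs and post-dose liver tests fall at times when PK blood is drawn anyway, liver events bring their own PK sample, and subjects lost to follow-up attend no visit. What the extra tube catches is mainly withdrawal between visits, and the documents give no withdrawal rate. All of this stands, and it limits the size of the point.

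The plan also leaves room for judgement. SAP 8.1.3 refers to current working practices and parameters as data permit, protocol 9.3.1 foresees exclusions with documented reasons, and population PK modelling is optional. A competent analyst might reject a lambda_z fitted to 24, 48 and 192 h, so the Day 7 and Day 14 terminal figures depend on the fitting rule. But none of these is a written rule, and a lambda_z standard would not repair AUC(0-t), which stays calculable from any short profile.

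A reader might infer that every withdrawal degrades the primary result, or that the error always runs one way. The table and the simulation do not support that for late withdrawals or for Cmax. Nor is the stated precision undermined: "The sample size of 20 to obtain 12 evaluable subjects has been chosen based on feasibility" is itself the allowance for losses. Evaluable is not defined, however, so a truncated subject could be counted among the 12. A reader might also infer biased B-cell results. These are shown by planned time and are not integrated over follow-up, so the pooling argument does not reach them.

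**Conclusion.** The point holds within limits. Followed as written, the plan forgoes recoverable primary-endpoint data at a visit that already draws blood, and it pools truncated profiles without a rule. AUC(0-t) is biased low when the last PK sample is before about Day 56. AUC(0-inf) and t1/2 are biased low, and CL high, when it is before about Day 21 to 28.

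The shifts for one subject in 12 are illustrations, not forecasts, since no withdrawal rate is given. The sizes rest on the protocol's half-lives, the assumed 40-70% distribution fraction and, for terminal parameters, a last-three-points fit. The pooling gap matters more than the missing sample. For B-cell subsets the loss is of data only. The study tests no hypothesis, so no error rate is at stake. The change is cheap and worth making.

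**What to change.** 1. Mark Blood PK sampling and Biological Markers in the Discontinuation column of protocol Table 2 and SAP 11.1.1, and record actual times. State that the PK sample is planned data and enters the non-compartmental analysis, which already uses actual times. State how the B-cell sample will be displayed, because SAP 11.3.3 leaves unscheduled visits out of tables and figures.
2. In SAP sections 5 and 8.1.4, keep all dosed subjects in the Cmax summary. Present AUC(0-t) with and without subjects who lack the Day 84 sample, or add an AUC over a common interval. Present AUC(0-inf), CL, Vz, lambda_z and t1/2 with and without subjects whose terminal phase is inadequately sampled, for example those with a last PK sample before Day 28. Flag these subjects in Listing 32. One cut-off would not suit both groups: at Day 28 AUC(0-inf) is nearly unbiased, while AUC(0-t) at Day 42 is still 14-17% below a completer's (r = 0.831-0.857).
3. Reconcile the timing of the liver-event PK sample between section 6.2.1 and Appendix 1.

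The cost is one or two tubes at a visit that already draws blood, edits to two schedules, one extra summary table and a smaller n in the restricted summaries.

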**Table 3 Time assessment window of the each PK sample collection**

Study Day	Hrs relative to dose	Blood sampling for PK
Day 0: pre-dose	Day 0 pre-dose	-60 minutes
Day 0: 5min	5min after dose completion	± 1 minutes
Day 0: 1hour	1 hour after dose completion	± 10 minutes
Day 0: 6 hour	6 hour after dose completion	± 15 minutes
Day 0: 24 hour	24 hour after dose completion	± 1 Hrs
Day 1	48 hour after dose completion	± 2 Hrs
Day 7	192 hour after dose completion	-48Hrs to +2 Hrs
Day 14	360 Hrs after dose completion	-48Hrs to +2 Hrs
Day 21	528 Hrs after dose completion	-48Hrs to +2 Hrs
Day 28	696 Hrs after dose completion	-48Hrs to +2 Hrs
Day 42	1032 Hrs after dose completion	-48Hrs to +2 Hrs
Day 56	1368 Hrs after dose completion	-48Hrs to +2 Hrs
Day 84	2040 Hrs after dose completion	-48Hrs to +2 Hrs

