### 3. STUDY DESIGN

#### 3.1. Study Schematic

#### 3.2. Study Design Detail

This will be a multicenter, single dose study of intravenous GSK1550188 at a dose of 10 mg/kg in Chinese subjects with SLE.

After the study has been explained to the subjects and they have given full informed consent, the subjects will undergo a medical screen within 30 days prior to the first dose, to determine their eligibility for participation based on the inclusion/exclusion criteria.

After screening, eligible Chinese SLE subjects will be admitted to the study center on Day 0. Each subject will receive the dose on Day 0 after completion of all the pre-dose procedure. The subjects will be kept in the study center up to 24 hours post dosing with subsequent outpatient visits occurring on Days 1, 7, 14, 21, 28, 42, 56, and 84.

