#### 3.3. Discussion of Study Design

##### 3.3.1. Design Rationale

This study is designed to assess the pharmacokinetics, safety, tolerability, and pharmacodynamics of a single intravenous 10mg/kg GSK1550188 dose in Chinese subjects with SLE. The study is open-label as the primary endpoint (pharmacokinetic parameters) will not be influenced by subjects knowing that they are receiving active treatment. The

subjects will have pharmacokinetic samples collected for 84 days (more than five half-lives) after dosing to enable a comprehensive pharmacokinetic profile to be generated. The pharmacokinetics of a single intravenous 10mg/kg GSK1550188 dose has never been assessed in healthy subjects, but has been assessed in Japanese (Study BEL114243) and Western subjects (Study LBSL01) with SLE. Therefore, Chinese subjects with SLE instead of Chinese healthy subjects will be recruited for this study to allow unbiased comparison between Chinese and non-Chinese subjects, if necessary.

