#### **6.2.2. Clinical Laboratory**

Blood and urine will be taken for clinical laboratory test at screening and at pre-dose, and Days 0, 1, 14, 28, 56 and 84 post-dose.

- Hematology: WBC, RBC, Hb, Ht, PT, PTT, platelet count and WBC-differential (including ESR on screening)
- Chemistry: AST, ALT, ALP, GGT, LDH, creatinine, BUN, total bilirubin, total protein, albumin, uric acid, glucose, sodium, potassium, magnesium, chloride, carbon dioxide, calcium, phosphate (including CRP on screening)
- Urinalysis: protein, glucose, ketones, occult blood, microscopic examination
- Spot urine for proteinuria assessment

Note: ALT and/or AST elevations of greater than 2.5 x ULN will require Hepatitis B assessment, see Section [6.2.1.1](#)

All clinical laboratory blood samples will be sent to a central laboratory for analysis (details provided in the SPM). The central laboratory will fax laboratory results to the Investigator and will transmit the results electronically to GlaxoSmithKline.

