#### **6.3. Pharmacokinetics**

Blood samples will be collected for PK at pre-dose, and at 5 minutes, 1, 6 and 24 hours, and Days 1, 7, 14, 21, 28, 42, 56 and 84 post-dose. The actual date and time of sampling will be recorded in the CRF. Serum will be harvested within one hour of blood sample collection. PK samples will be sent to a local bioanalytical laboratory and analyzed using a validated method (details provided in the SPM).

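### Table 3's nominal PK hours run exactly one day ahead of its day labels on all eight outpatient rows; in practice only the Day 1 sample is affected

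*Protocol*

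**What the plan says.** Protocol section 3.2 puts dosing on Day 0, and section 6 fixes the clock: "The end time of the infusion will be designated Time 0". Table 3, added by Amendment 01, then gives each PK sample a nominal time and a window.

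- The last Day 0 sample is at 24 h, ± 1 h.
- Day 1 is at "48 hour after dose completion", ± 2 h.
- Days 7, 14, 21, 28, 42, 56 and 84 are at 192, 360, 528, 696, 1032, 1368 and 2040 h, each with a window of -48 h to +2 h. The last row reads "2040 Hrs after dose completion".

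Section 6.3 lists 24 hours and Day 1 as different samples: "Blood samples will be collected for PK at pre-dose, and at 5 minutes, 1, 6 and 24 hours, and Days 1, 7", and so on to Day 84. Table 2 does the same, with 24 h as a column under Day 0 (Visit 2) and Day 1 as outpatient Visit 3. Section 3.3.1 describes PK sampling as lasting 84 days.

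On analysis, protocol 9.3.4.2.2 and SAP 8.1.3 base the non-compartmental parameters on actual sampling times. SAP 11.3.3 uses planned time for figures and summaries unless otherwise stated. It keeps visits outside the protocol windows, where recorded as deviations, in listings only, and leaves them out of figures, summaries and statistical analyses. SAP sections 2 and 3.1 tie the SAP to the protocol of 26 January 2016, which had no Table 3.

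**The concern.** With the dose on Day 0 and time counted from the end of infusion, a reader expects Day 1 at about 24 h, Day 7 at 168 h and Day 84 at 2016 h. Table 3 is a day later on every outpatient row and states no convention for it. PK is the primary objective and Table 3 is the stated sampling window, so the label and the hours should lead a site to the same draw.

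On the Day 1 row they do not. A site that follows the hours draws at 48 h. A site that follows the label draws close to 24 h, repeats the sample it has just taken, and has nothing further until Day 7. Under SAP 11.3.3, a mistimed draw recorded as a deviation would also leave every figure and summary, individual plots included, even though its actual time is known.

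**Working it through.** **1. Offset.** Inputs are the Table 3 hours and the Day 0 / end-of-infusion origin.

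| Day | Table 3 (h) | 24 x Day | 24 x (Day + 1) | Window (h) | Contains 24 x Day? |
|---|---|---|---|---|---|
| 1 | 48 | 24 | 48 | 46-50 | No |
| 7 | 192 | 168 | 192 | 144-194 | Yes |
| 14 | 360 | 336 | 360 | 312-362 | Yes |
| 21 | 528 | 504 | 528 | 480-530 | Yes |
| 28 | 696 | 672 | 696 | 648-698 | Yes |
| 42 | 1032 | 1008 | 1032 | 984-1034 | Yes |
| 56 | 1368 | 1344 | 1368 | 1320-1370 | Yes |
| 84 | 2040 | 2016 | 2040 | 1992-2042 | Yes |

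Table 3 equals 24 x (Day + 1) on 8 of 8 rows and 24 x Day on none. Counting from the start of a one-hour infusion makes the offset 25 h, so the choice of origin does not explain it.

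**2. Can label and window both be met?** Let the infusion end at clock time c hours on Day 0. Calendar Day d then runs from 24d - c to 24d + 24 - c hours.

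- Day 1: 24 - c to 48 - c overlaps 46-50 only if 48 - c > 46, that is, if the infusion ends before about 02:00. Otherwise the window falls on calendar Day 2. A draw at 24 h misses it by 46 - 24 = 22 h and lies inside the existing 23-25 h window.
- Days 7 to 84: the window runs from 24d - 24 to 24d + 26, which covers the whole labelled calendar day for any c from 0 to 24.

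**3. Gap if the 48 h sample is lost.** The next sample is in the Day 7 window, 144-194 h. The gap is 144 - 24 = 120 h to 194 - 24 = 170 h. Protocol 1.1.2 gives a distribution half-life of 1.1-1.8 days (26.4-43.2 h), so the gap spans 120/43.2 = 2.8 to 170/26.4 = 6.4 distribution half-lives.

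**4. Effect on AUC(0-∞).** Noiseless profile C(t) = s·2^(-t/Td) + (1 - s)·2^(-t/Tz), with:

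- Td = 1.1, 1.45 or 1.8 days (ends of the range from protocol 1.1.2, plus the midpoint) and Tz = 19.4 days (protocol 1.1.2, 10 mg/kg);
- s, the distribution share of the intercept, 0.30-0.60. This is an assumption; the documents give no value;
- terminal slope from the last three points; Day 1 draw at 46, 48 or 50 h; Day 7 draw at 144, 168, 192 or 194 h; later draws at 24 x Day or at the Table 3 hours.

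The documents name no trapezoid rule, so both are shown. AUC(0-∞) without the 48 h sample, relative to with it:

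- linear: +0.36% to +3.13%
- log: +0.24% to +2.14%

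The largest values occur at s = 0.60 and Td = 1.1 days.

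**5. Effect on the summary.** With 1 of 12 subjects affected, the geometric mean moves by 1.0313^(1/12) - 1 = 0.26% at most. With all 12 affected it moves by at most 3.1%. For scale, protocol 9.2.1 plans a 95% CI within 22.0% for AUC. This reproduces: log-scale SD = √ln(1 + 0.321²) = 0.313, t with 11 df = 2.201, exp(2.201 x 0.313/√12) - 1 = 22.0%. Cmax is unaffected.

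**The case against.** The strongest reply is that Table 3 follows one consistent, unstated convention: Day 0 runs to 24 h after dosing, and each later row marks the end of its labelled day. That reproduces all eight rows. It also fits Table 2, section 6.3, and section 3.2, where the stay comes first and Day 1 follows it: "The subjects will be kept in the study center up to 24 hours post dosing with subsequent outpatient visits occurring on Days 1, 7" and later days. The hours are printed on the same row as the label, so a site reading Table 3 would probably draw at 48 h. Most of this stands. It is good reason to think 48 h is intended. It does not remove the need to state the convention, because the Day 1 label and its window cannot ordinarily both be met.

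A reader might go further and infer that Day 1 means 24 h and that the hours are wrong. Three places seem to support this, and none does.

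- Table 2 footnote 10 allows subjects to be "discharged on Day 1 based on site flexibility and resource allocation". The footnote is attached to the discharge mark in the Day 0, 24 h column, so Day 1 reads as an alternative to that point.
- Section 6.2.2 lists laboratory draws "at pre-dose, and Days 0, 1, 14, 28, 56 and 84 post-dose". It names Day 0 and Day 1 separately, while Table 2 has a single post-dose laboratory mark before Day 14, under Day 0 at 24 h. That is a separate inconsistency in the laboratory schedule and says nothing about PK hours.
- The 84 days of section 3.3.1 against 2040/24 = 85 days is harmless, because 2016 h lies inside the Day 84 window.

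It is also fair to say that the AUC figures rest on an assumed distribution share and on a site actually misreading the row, and that the SAP points do not depend on the offset.

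**Conclusion.** The offset is certain and unexplained, but the point is minor. The documents do not show which of label and hours is wrong; the separate 24 h and Day 1 samples lean towards the labels. The practical conflict is confined to Day 1.

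The primary parameters are not shifted by the labelling itself, because they are computed from actual times. The remaining risk is one lost distribution-phase sample in a subject whose site follows the label. Given the bi-exponential profile and the assumed 30-60% share, that costs at most about 3% of that subject's AUC(0-∞), which is small beside the planned precision of 22.0%.

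The SAP rule is the more concrete analysis matter. Taken literally, omission from statistical analyses would discard valid concentrations with known times. That sits badly with the actual-time calculation in protocol 9.3.4.2.2 and SAP 8.1.3, with protocol section 9, which includes values verified as accurate, and with 9.3.2, which includes all available data.

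**What to change.** 1. Reconcile Table 3's day labels and hours with Table 2 and section 6.3, and state the convention. The sponsor chooses which to keep. Keeping the hours would mean labels of Days 2, 8, 15, 22, 29, 43, 57 and 85, or a note that each time marks the end of the labelled day. Keeping the labels would mean 24, 168, 336, 504, 672, 1008, 1344 and 2016 h, with Day 1 then duplicating the 24 h sample.
2. Update the SAP from the original protocol to Amendment 01, carrying the same planned times in hours.
3. In SAP 11.3.3, limit the out-of-window omission to mean and median summaries and profiles by nominal time, so that every valid concentration with a recorded actual time stays in the non-compartmental analysis and the individual plots.
4. Separately, align the Day 1 laboratory draw in section 6.2.2 with Table 2.

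For the PK point the cost is a clarification of one protocol table, an SAP version update and one SAP sentence. No extra samples are needed.
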